1 INTRODUCTION

This SAP defines the scope of the statistical analyses and provides a detailed description of the statistical methodology in order to support the final clinical study report (CSR).

2 PROTOCOL SUMMARY

2.1 Study objectives

2.1.1 Primary objective

To investigate the long-term safety and tolerability of brivaracetam (BRV) in pediatric study participants with Childhood Absence Epilepsy (CAE) or Juvenile Absence Epilepsy (JAE).

2.1.2 Secondary objective

To investigate long-term efficacy of BRV in pediatric study participants with CAE or JAE.

2.1.3 Other objectives

To investigate the long-term effect of BRV on behavior, cognition, and quality of life in pediatric study participants with CAE or JAE.

2.2 Study variables

2.2.1 Primary objective endpoints and estimands

Table 2-1: Primary objective

Objectives	Endpoints/estimands
To investigate the long-term safety and tolerability of BRV in pediatric study participants with CAE or JAE	
Treatment-emergent adverse events (TEAEs) 
Estimand: the estimand is defined by the following 4 attributes that will be used to define the treatment effect of interest for the primary safety analysis:
 
Population: population as defined in the protocol-specified inclusion/exclusion criteria reflecting the target patient population who receive at least 1 dose of BRV during the study.Study participant-level outcome: TEAE occurrence.Intercurrent event handling: The intercurrent event of concomitant medication use is handled by using a treatment policy strategy in which all TEAE data are included, regardless of receipt of any concomitant medication.The intercurrent event of treatment discontinuation is handled by using a while-on-treatment strategy where observation ends at 14 days after treatment is stopped. 
4. Population-level summary measure: incidence rates of TEAEs

Table 2-1: Primary objective

Objectives	Endpoints/estimands
To investigate the long-term safety and tolerability of BRV in pediatric study participants with CAE or JAE	
• TEAEs leading to discontinuation of study drug 
Estimand: the estimand is defined by the following 4 attributes that will be used to define the treatment effect of interest for the primary safety analysis:
 
1. Population: population as defined in the protocol-specified inclusion/exclusion criteria reflecting the target patient population who receive at least 1 dose of BRV during the study.2. Study participant-level outcome: TEAE leading to discontinuation occurrence.3. Intercurrent event handling: The intercurrent event of concomitant medication use is handled by using a treatment policy strategy in which all TEAE data are included, regardless of receipt of any concomitant medication.4. Population-level summary measure: incidence rates of TEAEs leading to discontinuation.
Primary objective	Secondary endpoints
To investigate the long-term safety and tolerability of BRV in pediatric study participants with CAE or JAE	
• Serious adverse events (SAEs)• Study drug-related TEAEs 
Estimand: the estimand is defined by the following 4 attributes that will be used to define the treatment effect of interest for the secondary safety analysis:
 
1. Population: population as defined in the protocol-specified inclusion/exclusion criteria reflecting the target patient population who receive at least 1 dose of BRV during the study.2. Study participant-level outcome: occurrence of events in the list above.3. Intercurrent event handling: The intercurrent event of concomitant medication use is handled by using a treatment policy strategy in which all TEAE data are included, regardless of receipt of any concomitant medication. 
The intercurrent event of treatment discontinuation is handled by using a while-on-treatment strategy where observation ends at 14 days after treatment is stopped.
 
4. Population-level summary measure: incidence rates.

Table 2-1: Primary objective

Objectives	Endpoints/estimands
Primary objective	Other endpoints
To investigate the long-term safety and tolerability of BRV in pediatric study participants with CAE or JAE	
TEAEs requiring a change in BRV doseMaximum intensity TEAE experienced (mild, moderate, and severe)Drug-related serious TEAEsFatal adverse events (AEs)TEAEs by maximum relationship (related and not related to BRV)SAEs by maximum relationship (related and not related to BRV) 
Occurrence of other seizure types, including generalized tonic-clonic seizures (GTCS), based on diary or EEG:
 
Non-absence seizures based on 1-hour EEGNon-absence seizures based on diary 
Estimand: the estimand is defined by the following 4 attributes that will be used to define the treatment effect of interest for the other safety analysis:
 
Population: population as defined in the protocol-specified inclusion/exclusion criteria reflecting the target patient population who receive at least 1 dose BRV during the study.Study participant-level outcome: occurrence of events in the list of endpoints above.Intercurrent event handling: the intercurrent event of concomitant medication use is handled by using a treatment policy strategy in which all AE/TEAE data or seizure data (as applicable) are included, regardless of receipt of any concomitant medication.Population-level summary measure: incidence rates. 
The intercurrent event of treatment discontinuation is handled by using a while-on-treatment strategy where observation ends at 14 days after treatment is stopped.

To investigate the long-term safety and tolerability of BRV in pediatric study participants with CAE or JAE	
CFB to each applicable visit in safety laboratory testsCFB to each applicable visit in electrocardiogram (ECG) parametersECG findings at each applicable visit

Table 2-1: Primary objective

Objectives	Endpoints/estimands
	
Physical and neurological examinations findings at each applicable visitPsychiatric and mental status at each applicable visitCFB to each applicable visit in vital signs (blood pressure, pulse rate, body temperature)CFB to each applicable visit in body weight and height

AE=adverse event, BRV=brivaracetam, CAE=childhood absence epilepsy, CFB=change from baseline, ECG=electrocardiogram, EEG=electroencephalogram, GTCS=generalized tonic-clonic seizure, JAE=juvenile absence epilepsy, SAE=serious adverse event, TEAE=treatment-emergent adverse event

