3 DATA ANALYSIS CONSIDERATIONS

3.1 Endpoints and statistical measures

Table 3-1: Study endpoints and statistical measures

Objective	Endpoint	Statistical measure(s)
Primary objective	Primary endpoint	
To investigate the long-term safety and tolerability of BRV in pediatric study participants with CAE or JAE	TEAEs	Incidence of TEAEs
	TEAEs leading to discontinuation of study drug	Incidence of TEAEs leading to discontinuation of study drug

Table 3-1: Study endpoints and statistical measures

Objective	Endpoint	Statistical measure(s)
Primary objective	Secondary endpoints	
To investigate the long-term safety and tolerability of BRV in pediatric study participants with CAE or JAE	SAEs	Incidence of serious TEAEs
	Study drug-related TEAEs	Incidence of study drug-related TEAEs
Primary objective	Other endpoints	
To investigate the long-term safety and tolerability of BRV in pediatric study participants with CAE or JAE	TEAEs requiring a change in BRV dose	Incidence of TEAEs requiring a change in BRV dose
	Maximum intensity TEAE experienced (mild, moderate, and severe)	Incidence of TEAEs by maximum intensity experienced
	Drug-related serious TEAEs	Incidence of drug-related serious TEAEs
	Fatal AEs	Incidence of fatal AEs
	TEAEs by maximum relationship (related and not related to BRV)	Incidence of TEAEs by maximum relationship to study drug
	SAEs by maximum relationship (related and not related to BRV)	Incidence of serious TEAEs by maximum relationship to study drug
	Non-absence seizures based on 1-hour EEG	Incidence of non-absence seizures based on EEG
	Non-absence seizures based on diary	Incidence of non-absence seizures based on diary
	CFB to each applicable visit in safety laboratory tests	Summary statistics of individual visit values and corresponding CFB to each visit

Table 3-1: Study endpoints and statistical measures

Objective	Endpoint	Statistical measure(s)
	CFB to each applicable visit in ECG parameters	Summary statistics of individual visit values and corresponding CFB to each visit
	ECG findings at each applicable visit	Incidence of ECGs which are abnormal clinically significant and abnormal not clinically significant
	Physical and neurological examinations findings at each applicable visit	Shift from Baseline neurological examinations findings which are abnormal clinically significant and abnormal not clinically significant. Physical examinations findings will be listed only

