3.2 General presentation of summaries and analyses

Statistical analysis and generation of tables, figures, study participant data listings, and statistical output will be carried out using SAS® Version 9.3 or higher. Descriptive statistics, such as the number of study participants with available measurements (n), mean, standard deviation (SD), median, minimum value, and maximum value for quantitative variables, and counts and percentages for categorical variables, will be provided. Unless otherwise noted, the denominator for percentages will be based on the set of study participants in the specified analysis set with at least 1 assessment at the time point or at least 1 assessment during the time interval being summarized.

Decimal places for descriptive statistics will always apply the following rules (with the exception of PK data):

- “ n ” will be an integer
- Mean, SD, and median will use 1 additional decimal place compared to the original data.
- Minimum and maximum will have the same number of decimal places as the original value.

The individual PK concentrations will be reported to 3 significant figures in the listing. The descriptive statistics will be rounded to 4 significant figures for the mean, geometric mean, median, SD, and confidence interval (CI), to 1 decimal place for geometric coefficient of variation and to 3 significant figures for the min, max.

Unless otherwise noted, all percentages will be displayed to 1 decimal place. No percentage will be displayed for zero counts, and no decimal will be presented when the percentage is 100%.

Unless otherwise specified (eg, for Baseline values), all outputs are based on data collected in EP0132 only, and do not include data collected in N01269. Data sources for the EP0132 EV are specified in [Section 3.3.6](#).

All outputs will be produced by actual syndrome (CAE/JAE) as reported in N01269 and for all participants. Adverse event outputs will be produced for the Evaluation Period and 3-month periods within the Evaluation Period. Selected outputs may also be produced by modal dose, maximum BRV dose, exposure duration, and 3-month periods during the Evaluation Period.

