10 SAFETY ANALYSES

10.1 Extent of exposure

The study medication duration for the Evaluation Period will be calculated as the date of the final dose of BRV during the Evaluation Period - the date of the first dose of BRV in EP0132 + 1 day. The Evaluation Period is defined in [Table 3-2](#). The overall duration of BRV for the entire study (including down-titration, if applicable) will be calculated as the date of the final dose of BRV - the date of the first dose of BRV in EP0132 + 1 day, where missing or partial date of last dose is handled as described in [Section 4.1.4.5](#).

Table 10-1: Exposure Duration Categories

Category	Duration
>0 months	≥ 1 day
≥ 3 months	≥ 90 days
≥ 6 months	≥ 180 days
≥ 12 months	≥ 360 days
≥ 18 months	≥ 540 days
≥ 24 months	≥ 720 days

Study medication duration for the Evaluation Period and for the entire study will be summarized descriptively for all participants, based on the SS, where study medication duration will be presented in months (1 month is equal to 30 days). In addition, cumulative exposure duration for the Evaluation Period will be summarized (number and percentage of participants). Percentages will be relative to the number of participants in the SS.

Study medication duration during the Evaluation Period will also be summarized categorically by modal dose category (>0.0 to <2.0 mg/kg/day, ≥ 2.0 to <3.0 mg/kg/day, ≥ 3.0 to <4.0 mg/kg/day, ≥ 4.0 mg/kg/day) and overall, based on the SS. Percentages for the modal dose categories will be relative to the number of participants in each exposure duration category. Percentages for the all participants will be relative to the number of participants in the SS. This table will also include participant years of exposure presented for all participants and by modaldose category. The participant years of exposure presented by modaldose category will be the total participant years of exposure of participants within that modaldose category.

Participant years of exposure will be calculated by summing the exposure duration in days for all participants in the Evaluation Period or in the modal dose category, and dividing the resulting value by 365.25.

BRV dosing occurring in clinic at the EV, MEV, FEV, YEV, UV as applicable, and EDV or FV as applicable will listed, indicating the visit, whether the study drug was administered, the date and time of administration, the medication formulation, and the single dosage amount (in mg or mL as applicable).

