10.2.1 AE summaries

An overall summary of TEAEs will provide the number and percentage of study participants with at least one: TEAE, serious TEAE, TEAE requiring dose change, drug-related TEAE, severe TEAE, TEAE leading to permanent discontinuation of study drug, AE leading to death (based on the All Participants Screened Set), and TEAE leading to death. This will be produced for the Overall Period and the Evaluation Period. Additionally, this summary will be presented by modal dose category for the Evaluation Period and for each 3-month period in the Evaluation Period.

Treatment-emergent AEs requiring a dose change will be identified from the AE eCRF where “Action Taken with Study Medication” is “Dose reduced” or “Dose increased”.

All AEs will be summarized overall and by MedDRA primary system organ class (SOC) and MedDRA preferred term (PT). The number and percentage of study participants experiencing each event at least once will be summarized. All summaries will be sorted alphabetically by SOC and by incidence of AEs within PTs, starting with the highest incidence overall. Only the first occurrence of a TEAE of a particular PT will be included in incidence calculations, but all occurrences of TEAEs of the same PT will be included in counts of TEAEs. All summaries will be produced for the Overall Period, Evaluation Period and for each 3-month period in the Evaluation Period except for the incidence of TEAEs leading to permanent discontinuation of study drug which will not be produced for the Overall Period.

The following summaries will be provided:

- Incidence of TEAEs
- Incidence of TEAEs leading to permanent discontinuation of study drug
- Incidence of serious TEAEs
- Incidence of TEAEs by relationship
 - Relationship is related/not related to study drug and is decided by the study investigator.
- Incidence of TEAEs by maximum relationship.
 - Related to study drug is considered more significant than not related to study drug ie, if a study participant has experienced the same TEAE on more than one occasion, where on at least one of the occasions it was considered to be related to the study drug, the maximum relationship is related.
- Incidence of TEAEs not exclusively related to COVID-19 vaccination
 - These will be identified as TEAEs where “Is the Event Related to a COVID-19 Vaccination” is answered “No” on the AE eCRF
- Incidence of TEAEs by maximum intensity

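### The safety estimands name incidence rates, but no adverse-event output has a person-time denominator, so the whole-period percentages depend on time in study

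*SAP*

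**What the plan says.** SAP 2.2.1 (Table 2-1) gives the two primary safety endpoints a yes/no outcome per participant; for the first it is "Study participant-level outcome: TEAE occurrence". The summary measure is "Population-level summary measure: incidence rates of TEAEs", and TEAEs leading to discontinuation use the same term. The secondary safety endpoints (SAEs, drug-related TEAEs) also name incidence rates. No time unit or person-time denominator is given.

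For the TEAE endpoint, "observation ends at 14 days after treatment is stopped". The estimand for TEAEs leading to discontinuation has no such clause. Protocol 4.2 applies the while-on-treatment strategy to the TEAE primary endpoint only, and SAP 10.2 exempts TEAEs leading to discontinuation from the 14-day cut-off.

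SAP 3.1 (Table 3-1) drops the word rate; the measure for the second endpoint becomes "Incidence of TEAEs leading to discontinuation of study drug". SAP 10.2.1 states the output: "The number and percentage of study participants experiencing each event at least once will be summarized". It adds that "all occurrences of TEAEs of the same PT will be included in counts of TEAEs". The default denominator in SAP 3.2 is people: "Unless otherwise noted, the denominator for percentages will be based on the set of study participants in the specified analysis set", limited to those with an assessment in the interval.

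Person-time appears in SAP 10.1: "Participant years of exposure will be calculated by summing the exposure duration in days for all participants in the Evaluation Period", or in a modal-dose category, and dividing by 365.25. It feeds the exposure table only.

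TEAE tables are planned for the Overall Period, the Evaluation Period and each 90-day period (SAP 10.2, 10.2.1). A participant enters a 90-day table only if their Evaluation Period reaches its first day (SAP 3.3.3). All outputs are also split by CAE/JAE (SAP 3.2), and the overall TEAE summary is split by modal dose (SAP 10.2.1).

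**The concern.** A percentage with at least one event has a clear meaning when everyone is observed for the same time. Here they are not. One dose puts a participant in the Safety Set (SAP 3.7.2). Protocol 4.1 gives a two-year minimum but lists several alternative end conditions, whichever comes first. The SAP has rules for early discontinuation and for a Final Visit before Month 24 (3.13.2, 3.13.4). Efficacy is truncated at Month 24 (3.12.2, 8.1), while safety data after Month 24 are kept (3.3.3). The primary safety result thus has neither a common horizon nor an adjustment for exposure.

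Three planned outputs inherit this:
- **CAE versus JAE.** Any difference in time in study enters the contrast.
- **Modal dose over the Evaluation Period.** Everyone starts at 2.0 mg/kg/day or its equivalent, and ties go to the lower category (SAP 3.3.10). A higher modal category needs more days there than in any other, so dose group can be linked to time in study.
- **The 5% threshold for non-serious TEAEs** (SAP 10.2.1). It becomes easier to cross as follow-up lengthens.

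**Working it through.** There is no plan figure to reproduce. The documents state no expected TEAE rate, dropout share or follow-up distribution, and the approximately 140 participants are a rollover expectation (SAP 2.4). The hazards and dropout shares below are assumptions; the day counts are from SAP Tables 3-3 and 3-5.

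**Formulas.** With a constant first-event hazard r per participant-year and follow-up of T years for all, crude percentage = 1 - exp(-rT). With exponential dropout at hazard L, crude percentage = r/(r+L) x [1 - exp(-(r+L)T)]. Expected time at risk per participant is [1 - exp(-(r+L)T)]/(r+L), so first events divided by time at risk equals r in every case.

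**One year versus three years, same rate.**
- r = 0.2: 1 - exp(-0.2) = 18% and 1 - exp(-0.6) = 45%, a gap of 27 points.
- r = 0.4: 1 - exp(-0.4) = 33% and 1 - exp(-1.2) = 70%, a gap of 37 points.

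**Whole-period percentage under different follow-up.** Month 24 is 731/365.25 = 2.00 years and Month 36 is 1096/365.25 = 3.00 years. For a share d leaving by Month 24, L = -ln(1-d)/2.00.

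| Follow-up (assumed) | Mean years | r = 0.1 | r = 0.5 | r = 2.0 |
|---|---|---|---|---|
| 80% leave by Month 24 | 0.99 | 9.2% | 35.5% | 71.1% |
| 40% leave by Month 24 | 1.57 | 14.3% | 51.6% | 87.7% |
| All stay to Month 24 | 2.00 | 18.1% | 63.2% | 98.2% |
| All stay to Month 36 | 3.00 | 25.9% | 77.7% | 99.8% |

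The first-event rate per participant-year is unchanged down each column (0.10, 0.50, 2.00).

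**A 90-day table, limited to those who enter the period.** At r = 0.5 and T = 90/365.25 = 0.246 years, the percentage is 11.6% with no dropout, 11.2% at the 40% dropout rate and 10.5% at the 80% rate. Most of the dependence is gone; what remains is partial exposure in the last period.

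**Can the planned participant-years serve as denominator?** Not unchanged. They sum dosing days in the Evaluation Period, stop at the last dose there and continue after a participant's first event. A first-event rate needs time that stops at the first event and otherwise runs to the end of the window in which events are counted.

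**The case against.** The strongest reply is that the plan already has a time-aligned analysis. The 3-month tables have fixed length and restricted denominators, and they are given by syndrome and, for the overall summary, by modal dose. That stands, so a reader who infers that the SAP offers only crude percentages with no time basis goes too far. The tables still do not give the whole-period result. One participant can count in several periods, so they cannot be added up; someone present for one day of a period counts as fully at risk; and they leave out the Down-Titration and Safety Periods.

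Second, incidence rates may simply be loose wording for a proportion: the outcome is binary, no time unit is given, and Table 3-1 says incidence. This is plausible, so the documents do not prove that the analysis departs from a person-time estimand. A proportion would still need a stated horizon, and none is given.

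Third, a reader might infer that follow-up is very unequal, or that CAE/JAE or dose groups differ in exposure. The documents show only that it can vary. SAP 3.3.3 speaks of a subset past Month 24, and a rationale in the SAP version history calls it small.

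Fourth, event counts and Evaluation Period participant-years are both reported, so a reader could form an approximate event rate. That is correct, but it counts repeat events, carries no confidence interval and does not match the Overall Period.

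Finally, a first-event rate is itself free of follow-up length only if the hazard is roughly constant. This also stands, and is why the 3-month tables should be read beside it.

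**Conclusion.** The point holds as a gap between the named measure and the planned output, and as a limit on how the whole-period TEAE percentages can be read. They depend on time in study, overall and within the CAE/JAE and modal-dose splits.

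Its size in this trial is unknown. The 27 to 37 points and the table of scenarios are illustrations under assumed constant hazards and follow-up, not estimates of bias. The one-year versus three-year contrast in particular is not a feature that the documents attribute to any group.

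Nor do the documents support treating both primary endpoints as while-on-treatment. TEAEs leading to discontinuation are exempt, so a uniform cut-off at last dose plus 14 days would be wrong for them. The study is single-arm and descriptive with no hypothesis test, so no type I error or power is affected. This is an inexpensive improvement to the primary safety reporting.

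**What to change.** - **Add a rate.** In the overall TEAE summary, for the Overall and Evaluation Periods and by modal dose for the Evaluation Period, report participants with a first event per 100 participant-years at risk, with 95% confidence intervals. Cover at least TEAEs, serious TEAEs, drug-related TEAEs and TEAEs leading to discontinuation.
- **Define time at risk.** Run from first dose in EP0132 to the first event of that type or, if none, to the end of the matching event window. For all types except TEAEs leading to discontinuation, that window ends at last dose plus 14 days, or at the end of the reporting period if earlier. State a separate window for TEAEs leading to discontinuation.
- **Label the rest.** Keep the crude percentages and the 3-month tables, call the percentages incidence proportions, and make the term in Table 2-1 agree with Table 3-1 and SAP 10.2.1.

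The cost is SAP wording and one time-at-risk derivation per event type and period, with no new data. State the constant-hazard caveat and read the rate alongside the 3-month tables.
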